## 1. SYNOPSIS

[figure not shown]
Study Title	COVID-19 Virtual Post Intensive Care Syndrome (CoV-PICS) Clinic: Modern, Convenient and Practical Recovery Care.
Objective	To determine if discharged COVID-19 patients with PICS symptoms are willing and able to navigate the technology necessary to participate in a virtual outpatient clinic (feasibility and acceptance). To determine if a multidisciplinary group of professionals, familiar with PICS, are able to interpret information obtained from virtual visits and patient self-reported surveys to make recommendations for future care based on baseline and changes in patient symptoms over time (feasibility). To determine the ease of receiving and receptiveness of primary care physicians to a summary of clinic recommendations (feasibility and acceptance). To determine if the PICS symptoms and patient characteristics of patients with an ICU stay due to COVID-19 are similar to those reported in the literature of non-COVID-19 patients.
Study Period	Planned enrollment duration: Aug 2020 – Feb 2021  Planned study duration: Aug 2020 – Aug 2021
Number of Patients	80, adult (minimum age 18, no maximum)
Study Treatment	None
Study Design	Observational feasibility trial
Inclusion and Exclusion Criteria	
Inclusion Criteria:
 
 
1. Patients who are at least 18 years of age
 
2. COVID-19 diagnosis with a stay in the intensive care unit at BJH
 
3. Missouri resident
 
 
Exclusion Criteria:
 
 
1. Severe cognitive deficits or dementia prior to hospitalization
 
2. Long-term resident of a skilled nursing facility prior to admission
 
3. Non-English speaking (will not have an interpreter available)
 
4. Hospice or Comfort Care at discharge
 
5. No plans to return to some degree of independent living at the time of discharge
 
6. Pregnant or a prisoner at the time of discharge
 
7. Blind or deaf
 

CONFIDENTIAL: This document is the intellectual property of [name]. Acceptance of this document constitutes the agreement by the recipient that no unpublished information contained herein will be published or disclosed without prior written approval.

	If during the consent process if it is determined the patient will not have a home internet connection or smartphone access for the virtual clinic; or displays the inability to use either a computer or phone for virtual appointments, they will also be excluded from enrollment.
Measurements	
Primary outcomes:
 
 
1. Patient adherence and determination of feasibility and acceptance with the virtual clinic and telehealth visits based on the FIM® (feasibility of intervention measure), IAM® (intervention appropriateness measure) and the AIM® (acceptance of intervention measure)
 
2. Patient attendance record
 
3. Number of on-time arrivals to the virtual visit
 
4. Number of patient successfully completed online questionnaires after initial training.
 
5. Patient primary care or clinic physician feedback using the tools in #1 and open ended comments.
 
 
Secondary outcomes: (to compare patient characteristics to historical non-COVID-19 patients with PICS)
 
 
1. ICU Memory Tool® (measures recall and aids in our understanding of the quality of life)
 
2. PROMIS®29 Profile (measures anxiety, depression, fatigue, pain, physical function, sleep and ability to participate in social roles),
 
3. MOCA-5 minute® (measures cognitive function),
 
4. Katz and Lawton® (measures activities of daily living),
 
5. PG-SGA short form® (screens for malnutrition risk),
 
6. Five-time sit-to-stand, and Two-minute step test.
 

Statistical Methodology	
Descriptive statistics will be used to summarize the data. Continuous variables will be reported as medians and interquartile ranges or means and standard deviations as appropriate. Categorical variables will be reported as frequencies and percentages. Changes in the scores or times of the ICU Memory Tool®, PROMIS®29 Profile, MOCA-5 minute, Katz and Lawton®, PG-SGA short form®, Five time sit-to-stand and Two-minute step test, from hospital discharge to 3- and 6-month post discharge will be estimated using the Wilcoxon Signed Rank Test (non-parametric alternative to t-test) and compared across different categorical variables (e.g. age, gender, discharged directly to home, 30-day readmission) using ANOVA and continuous variables (e.g. APACHE IV, ICU length of stay) using ANCOVA.
 
A consensus sample would be optimal in this feasibility study (all patients meeting criteria consented and participated), however since that

CONFIDENTIAL: This document is the intellectual property of [name]. Acceptance of this document constitutes the agreement by the recipient that no unpublished information contained herein will be published or disclosed without prior written approval.

	
is unlikely, a convenience sample will be used. The future of patients with COVID-19 disease requiring ICU admission is uncertain. A conservative estimate of 50% of these patients will develop PICS. In the first month at BJH, 29 patients were discharged from the ICU. This translates into approximately 15 patients per month. Although this number may increase or decrease due to uncertainties surrounding the disease. Previous studies (see literature review) suggest care for PICS should begin within 12 weeks of discharge. Therefore once IRB approval is obtained, patients discharged within the past 10 weeks will be screened for possible participation. A post-hoc power analysis will be done.

--	---

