Day 1-2  Week 10 post initial visit And Week 22 post initial visit	
RC: If patient not enrolled in MyChart or has forgotten how to access, call patient and walk them through obtaining access. Direct link (attached to the patient’s study ID) will be emailed or texted (per patient preference) to access the following surveys, requesting one week turn-around time:
 
ICU Memory Tool® (measures recall and aids in our understanding of quality of life)
 
PROMIS®29 Profile (measures anxiety, depression, fatigue, pain, physical function, sleep and ability to participate in social roles)
 
MOCA-5 minute® (measures cognitive function)
 
PG-SGA short form® (screens for malnutrition risk)

Day 2-9  Week 11 and Week 23 post initial visit	
RC: Will send form email from PI to PCP (if patient agreed to share information) providing an overview of the study (see attached)
 
RC will obtain notice from RedCap when surveys opened. RC will check completeness of survey responses. If surveys not completed within 5 days, send reminder email. If not completed in 7 days, call patient offering to administer surveys over the phone.

Day 11  Week 11 and Week 23 post initial visit	
RC: If patient does not complete surveys within 7 days of receipt and has not responded to phone calls; considered an enrollment fail (start of study) or withdrawal from study (repeat surveys), document on enrollment log.

Day 2-11  Week 11 and Week 23 post initial visit	
RC: If surveys completed, send thank you email. Email and/or call patient to schedule first virtual visit. Email link to research team members for them to review responses in RedCap.

Day 9 – 18  Week 12 and Week 24 post initial visit	
RC: Schedule initial 60-75 minute virtual assessment based on MD schedule. Email all team members to obtain availability in non-physician visit time. Send outlook calendar appointments to team members. All providers engaging in telehealth visits will be licensed in the state where the participant lives.

1-2 days before virtual team visit	
RC: Send reminder email to research team members who will be on the visit. Send agenda for call – member/time slot. Send instructions/link for team members to join the virtual visit. Email the patient the instructions on how to access the virtual appointment in MyChart or the HIPPA approved WashU ZOOM link.

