### **2.4.6.4 Secondary Outcome Measures**

[figure not shown]
Secondary outcomes: (to compare patient characteristics to historical non-COVID-19 patients with PICS)

1. ICU Memory Tool® (measures recall and aids in our understanding of the quality of life)
2. PROMIS®29 Profile (measures anxiety, depression, fatigue, pain, physical function, sleep and ability to participate in social roles),
3. MOCA-5 minute® (measures cognitive function),
4. Katz and Lawton® (measures activities of daily living),
5. PG-SGA short form® (screens for malnutrition risk),
6. Five-time sit-to-stand, and Two-minute step test.

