### **2.4.6.5 Statistical Methods**

Descriptive statistics will be used to summarize the data. Continuous variables will be reported as medians and interquartile ranges or means and standard deviations as appropriate. Categorical variables will be reported as frequencies and percentages. Changes in the scores or times of the ICU Memory Tool®, PROMIS®29 Profile, MOCA-5 minute, Katz and Lawton®, PG-SGA short form®, Five time sit-to-stand and Two-minute step test, from hospital discharge to 3- and 6-month post discharge will be estimated using the Wilcoxon Signed Rank Test (non-parametric alternative to t-test) and compared across different categorical variables (e.g. age, gender, discharged directly to

CONFIDENTIAL: This document is the intellectual property of [name]. Acceptance of this document constitutes the agreement by the recipient that no unpublished information contained herein will be published or disclosed without prior written approval.

home, 30-day readmission) using ANOVA and continuous variables (e.g. APACHE IV, ICU length of stay) using ANCOVA.

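### The MOCA-5 minute is given three times with no alternate version and no retest allowance, so a rise in the overall score cannot be separated from practice

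*Combined protocol and SAP*

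**What the plan says.** Section 2.4.6.4 lists "MOCA-5 minute® (measures cognitive function") among the secondary outcomes. It is the only instrument there described as measuring cognition.

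The table in section 2.4.1 sends one survey set, including this test, at Day 1-2 and then at "Week 10 post initial visit And Week 22 post initial visit". The instrument is named once for all three rounds, with no version, form or rotation given.

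The Synopsis, repeated in section 2.4.6.5, says that "Changes in the scores or times of the ICU Memory Tool®, PROMIS®29 Profile, MOCA-5 minute" and the remaining secondary instruments, "from hospital discharge to 3- and 6-month post discharge", "will be estimated using the Wilcoxon Signed Rank Test (non-parametric alternative to t-test"). The changes are then compared across categorical factors by ANOVA and against continuous factors by ANCOVA.

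The Synopsis describes the design as "Observational feasibility trial", with no study treatment. There is one cohort and no concurrent comparator. The stated purpose of the secondary outcomes is comparison with historical non-COVID-19 patients with PICS.

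**The concern.** Most of the other repeated instruments are self-reports, functional scales or physical tests. The MOCA-5 minute scores answers to cognitive items, so a patient who has met the items before may score higher without any change in cognition. With no second group tested on the same schedule, nothing removes such a gain from the overall change. The signed-rank test asks only whether scores shifted.

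Cognition is one of the three PICS components in section 2.1. The preliminary data in 2.1.1 say that cognitive impairment can last for months to years after ICU discharge. Little true change over six months is therefore plausible on the protocol's own account, and that is when a modest practice gain would mislead most.

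**Working it through.** **Schedule.** The first test is sent on Day 1-2. The initial visit falls on Day 9-18 ("Schedule initial 60-75 minute virtual assessment based on MD schedule"), so it comes 9 − 2 = 7 to 18 − 1 = 17 days after the first test.
- Second test: 7 + 70 = 77 to 17 + 70 = 87 days after the first, which is 11.0 to 12.4 weeks.
- Third test: 7 + 154 = 161 to 17 + 154 = 171 days after the first, which is 5.3 to 5.6 months.

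**What the plan quantifies.** It plans 80 patients but gives no alpha, power, SD, expected change or retest correlation. There is no figure of its own to reproduce here.

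**Illustration.** Every input below is an assumption: true change zero; practice gain g of 0.1 to 0.4 SD of the score; retest correlation r of 0.6 or 0.8; 50 or 65 complete pairs; two-sided 5%; normally distributed changes.

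The SD of change is √(2(1 − r)): √0.8 = 0.894 for r = 0.6 and √0.4 = 0.632 for r = 0.8, in units of the score SD. The standardised gain is δ = g/√(2(1 − r)). The approximate chance of a significant improvement is Φ(δ√n − 1.96).

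- Weakest case, g = 0.1, r = 0.6, n = 50: δ = 0.112, δ√n = 0.79, Φ(−1.17) = 12%.
- Strongest case, g = 0.4, r = 0.8, n = 65: δ = 0.632, δ√n = 5.10, Φ(3.14) = 99.9%.

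In the table, each range runs from r = 0.6, n = 50 to r = 0.8, n = 65. The last column simulates the signed-rank test itself (10,000 runs per setting), counting improvements only.

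| Assumed gain (SD) | Normal approximation | Simulated signed-rank |
|---|---|---|
| 0 | 2.5% | about 2.5% (5% counting both directions) |
| 0.1 | 12-25% | 11-23% |
| 0.2 | 35-72% | 33-69% |
| 0.3 | 66-97% | 61-96% |
| 0.4 | 89% to over 99% | 86% to over 99% |

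**With all 80 patients.** A mean change of 1.96/√80 = 0.219 SD of change reaches p < 0.05, whatever its source. In score SDs that is 0.219 × 0.894 = 0.20 (r = 0.6) or 0.219 × 0.632 = 0.14 (r = 0.8).

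**Which results are exposed.** If every patient gains the same amount g, the difference in mean change between two groups is (Δ₁ + g) − (Δ₂ + g) = Δ₁ − Δ₂, so g cancels. The first-round score precedes any repetition within the study. Only the overall change from the first round carries the gain in full.

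**The case against.** Several stronger readings are tempting, and the documents do not support them.

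- *The identical form is reused.* The protocol names the instrument, not the form, and several attachments are outside the text. What stands is that no version is specified, so reuse of one form is permitted.
- *The plan reads a rise as recovery.* It does not use that word for the change. It opens with descriptive statistics and says changes will be estimated. There is no study treatment, so no treatment effect is inflated.
- *A practice gain exists.* Nothing in the documents shows one or gives its size. Retests are 11 to 12 weeks apart at the first repeat, in patients who may be cognitively impaired, so a gain near zero is not excluded. The score of a short screening test is also discrete and bounded, unlike the simulated changes.
- *The historical comparison is distorted.* The plan does not say which round is set against the literature, and the first-round score is available for it.
- *Change from Week 10 to Week 22 is safer.* The documents give no basis for treating it as less affected by practice.

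It is also fair to say that the same change score has other weaknesses. Patients discharged within the past 10 weeks may be screened, so the first score may come well after discharge. The mode may switch between rounds ("If not completed in 7 days, call patient offering to administer surveys over the phone"). Patients who do not complete the repeat surveys are withdrawn. Dealing with practice alone would not make the change fully interpretable.

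These objections narrow the point without removing it: the overall change is tested, and the plan has no means of separating practice from true change.

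**Conclusion.** The concern holds for the overall within-patient change in the MOCA-5 minute. A rise cannot be attributed to cognitive change, because no alternate version, retest allowance or comparator is planned.

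The size is unknown. Under the stated assumptions, the chance of a significant improvement with no true change runs from roughly 10% to 99%, and it falls to the nominal rate if there is no gain. These figures show how sensitive the test is to a modest gain; they do not estimate what will happen.

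The first-round level is unaffected, as are between-group comparisons of change where the gain is common. No primary feasibility outcome uses the score. Severity is minor.

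**What to change.** In section 2.4.1, assign a different equivalent version of the MOCA-5 minute at each of the three rounds. Rotate the order across patients so that version and round are not confounded, and record the version used.

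The documents do not say whether equivalent versions are available to the study. If they are not, amend section 2.4.6.5 to:
- report the MOCA-5 minute as a level at each round;
- use the first-round score for the historical comparison;
- present the change as descriptive;
- state that a rise from the first round may reflect practice and is not read as cognitive recovery.

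The first option costs two further survey builds and a little version-to-version variance. The second costs a few sentences. Neither needs an extra visit or staff. The choice should be made before the first round, because without a comparator a practice gain cannot be removed afterwards.

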### **2.4.1 Study Procedures**

[figure not shown]
Study Procedures – Patient and PCP involvement	
Consent	Verbal consent is being sought. RC will be in a private space and obtain consent. All visits with the patient will be “virtual”.
Chart Review	Once patient consent is obtained, a prospective or retrospective chart review (depending on availability of research team members) will be conducted to obtain several data points (see attached).
Day 1	RC: Add patient to enrollment log: Study ID, first name, 3 letters of last name, MRN#, hospital discharge date, date returned home (if different from discharge date), and patient preferred email and phone number. If patient consents, PCP name, office phone number and fax number. This will be in a password protected Excel file available only to research team members.
Day 1	RC: Document date/time of consent, upload pdf of note to RedCap

CONFIDENTIAL: This document is the intellectual property of [name]. Acceptance of this document constitutes the agreement by the recipient that no unpublished information contained herein will be published or disclosed without prior written approval.

[figure not shown]
Day 1	
RC: Patient emailed a copy of the verbal consent, as well as, an information sheet, including a timeline for the study and “what to expect” and “what not to expect”.
 
What to expect: Timeline for study, Initial surveys, follow up surveys at 3 and 6 months, team visits (when – at minimum every 12 weeks; time commitment – 60-75 minutes), bi-weekly touch base email by RCs, individual visits with team members if warranted, summary of team recommendations after each visit, potential contact from PCP (if patient consented for information to be shared) and contact information for RC and PI for any questions or concerns throughout the study period. All providers engaging in telehealth visits will be licensed in the state where the participant lives.
 
What not to expect: Clinic physicians or other providers to write prescriptions, order lab tests or perform any treatments

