CONFIDENTIAL: This document is the intellectual property of [name]. Acceptance of this document constitutes the agreement by the recipient that no unpublished information contained herein will be published or disclosed without prior written approval.

30 min before each virtual team visit	RC: Email/call patient to address any concerns/questions regarding accessing virtual visit. RC will be “host” of the link for the visit.
Time of virtual team visit	RC: Send text to research team that patient has successfully entered the virtual visit.
During virtual team Visit	RC will function as timekeeper – send “chats or texts” to research team members to keep them on time. Team members will speak one at a time, with other members on mute. MD will start with introduction and overview that summary of recommendations after the visit will be sent to the patient’s PCP and the patient, emphasizing the patient and the PCP will be responsible for implementing and monitoring recommended treatments. Each professional will follow with introduction/any additional questions. The physical therapist and occupational therapist will go last to complete the following if the patient agrees/is able: Katz and Lawton® (measures activities of daily living) Five time sit-to-stand Two minute step test All providers engaging in telehealth visits will be licensed in the state where the participant lives.
1-3 days post virtual team visit	Team Members: responsible for documenting in EPIC their note/summary within 2 days of visit RC: Email patient summary of recommendations are available in MyChart for patient to access. Email PCP that summary is available in MyChart, or fax summary if PCP does not have access to MyChart. Clinic MD may choose to contact PCP personally regarding patient evaluation if they deem necessary.
2, 4, 6, 8, 10 weeks post initial and second virtual team visit	RC: Phone call to patient – What recommendations have been implemented? Any questions for any member of the research team? Any team member: may touch-base with the patient or treating professional (home physical therapist) if recommendations have been implemented by the PCP (e.g. physical therapy, change in medication, change in diet) to determine if they have any questions regarding the treatment initiated. If team member desires a virtual visit with patient – RC will host.

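### Secondary change scores are defined from hospital discharge, but no study score is scheduled then; restate the start as the first study score, and analyse age as continuous

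*Combined protocol and SAP*

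**What the plan says.** The Synopsis (Statistical Methodology) and section 2.4.6.5 carry the same text. Changes in seven listed measures "from hospital discharge to 3- and 6-month post discharge will be estimated using the Wilcoxon Signed Rank Test". The changes are then "compared across different categorical variables (e.g. age, gender, discharged directly to home, 30-day readmission) using ANOVA", and related to APACHE IV and ICU length of stay by ANCOVA: "using ANOVA and continuous variables (e.g. APACHE IV, ICU length of stay) using ANCOVA". No age bands are given, and no reason for treating age as categorical.

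Section 2.4.1 sets a different clock. Links to the ICU Memory Tool, PROMIS-29, MOCA and PG-SGA go out on Day 1-2 of the study, with one week asked for completion. They go out again at "Week 10 post initial visit And Week 22 post initial visit". Katz and Lawton, sit-to-stand and the step test belong to the virtual team visit: "The physical therapist and occupational therapist will go last to complete the following if the patient agrees/is able". The first of these visits is in the Day 9-18 row, and the later ones are at "Week 12 and Week 24 post initial visit". The enrollment log records "hospital discharge date, date returned home (if different from discharge date").

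Section 2.4.6.6 allows screening of patients discharged up to 10 weeks before IRB approval.

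**The concern.** The analysis counts time from discharge, while the schedule counts it from consent and then from the first visit. The two agree only for patients enrolled at about the time of discharge. For a patient enrolled late, the first score already contains several weeks of recovery, and the repeat labelled 3 months is closer to 6 months after discharge. Pooling such patients with early ones under the label of change from discharge misdescribes the result. Two analysts could also build different datasets from the same text.

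The group comparisons inherit the problem. If one group (for example, patients not discharged directly home) tends to be enrolled later, its first scores are taken later in recovery, and its change can differ for that reason alone.

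The age point is separate. Banding a continuous variable loses information, and with no bands stated they could be chosen after the data are seen.

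**Working it through.** **Timing.** The plan gives no figure for time from discharge to each score, so it is derived here. Inputs: consent at week 0 or week 10 after discharge (the 10 is from section 2.4.6.6; applying it to all enrolment is an assumption); survey links on Day 1-2, with a non-responder counted as an enrollment failure at Day 11; first visit on Day 9-18, reading that row as the visit date; repeat surveys at 10 and 22 weeks and repeat visits at 12 and 24 weeks after the first visit (section 2.4.1). Study days are counted from consent. Calling the consent day Day 1 would take one day off each result.

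Weeks after discharge = consent week + study day / 7 + weeks after first visit.

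| Score | Consent at week 0 | Consent at week 10 |
|---|---|---|
| First surveys (Day 1 to 11) | 0.1 to 1.6 | 10.1 to 11.6 |
| First physical and daily-living measures (Day 9 to 18) | 1.3 to 2.6 | 11.3 to 12.6 |
| Week 10 surveys sent | 11.3 to 12.6 | 21.3 to 22.6 |
| Week 12 visit | 13.3 to 14.6 | 23.3 to 24.6 |
| Week 22 surveys sent | 23.3 to 24.6 | 33.3 to 34.6 |
| Week 24 visit | 25.3 to 26.6 | 35.3 to 36.6 |

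Example: the latest first visit is 10 + 18/7 = 12.6 weeks, or 70 + 18 = 88 days. Three months is 52/4 = 13 weeks, so this patient's starting physical tests fall almost at the nominal 3-month point. The same patient's Week 10 survey, at 22.6 weeks, is 9.6 weeks past 3 months and 3.4 weeks short of 6 months (26 weeks). The early patient fits the labels fairly well; the late one does not.

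**What an enrolment lag can do to a group comparison.** All inputs are assumed: 40 v 40, unit SD, first score rising 0.1 SD per week since discharge, later score unrelated to that time, correlation 0.5, and one group's first score on average 2 weeks later (uniform 2-10 v 0-8 weeks). There is no other group difference. The expected difference in mean change is 0.1 x 2 = 0.2 SD. In 20,000 simulated studies, two-group ANOVA on change rejects in 14% at a nominal 5%. With weeks since discharge as a covariate it rejects in 5%, and the mean difference is about 0.

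**Age.** Assumed: normally distributed age, linear correlation r = 0.3 with change, two-sided 5%, equal-sized bands.

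| Age analysed as | Power, n = 80 | Power, n = 60 |
|---|---|---|
| Continuous | 78% | 66% |
| Median split | 58% | 47% |
| Thirds | 57% | 44% |
| Quarters | 53% | 41% |

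These come from 20,000 simulations each. The noncentral F formula at n = 80 gives 79.3, 58.5, 57.6 and 54.4%. A median split of a normal variable keeps 2/pi = 64% of the information, so 80 patients act like 80 x 0.64 = 51. If the best of three cut-points is chosen after the data are seen, the 5% false-positive rate rises to about 11%.

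**The case against.** *A reader might infer a larger fault: that ANOVA on change is wrong in non-randomised groups because no baseline term is named.* The documents do not support that. The plan states its question, difference in mean change, and ANOVA answers it. No objective asks whether patients with equal starting scores recover differently. Nor is the adjusted model safer by default. Assume a 0.5 SD baseline gap, correlation 0.5 and 40 v 40. If follow-up depends only on the first score, the change analysis rejects in about 20% of studies although there is no difference at equal baseline. If the group means are stable, the adjusted model rejects in about 23% although mean change is equal. The documents cannot say which case applies, and reporting both models doubles the number of exploratory estimates.

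*The 10-week window describes patients already discharged at IRB approval.* This is correct. Patients discharged later may be enrolled at once, and the week 0 column then applies. The mismatch would shrink for them, but the planned cohort can include both kinds, and even at week 0 nothing is scored at discharge.

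*Discharge scores or age bands may exist elsewhere.* The linked inpatient study covers nutrition and mobility, and the data attachment was not available. Age bands could be set there. But nothing in the protocol says that these instruments are given at discharge, and section 2.4.1 presents the first surveys as the start of data collection.

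*Continuous age is a preference.* Partly so. The power gain assumes a linear relation, and the study has no power target. What stands is that the plan treats APACHE IV and length of stay as continuous and gives no reason to treat age otherwise.

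**Conclusion.** Two things hold. First, the stated start of change contradicts the visit schedule, and the passages must be reconciled. This rests on the text alone; only the size of the mismatch depends on the assumed consent window of 0 to 10 weeks and on reading Day 9-18 as the date of the first visit. Second, listing age as categorical without bands is an avoidable loss of information, of about 20 to 25 percentage points of power under the assumed r = 0.3.

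The ANOVA on change is not an error. A baseline-adjusted comparison beside it is optional.

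The point is minor. These are secondary scores in a feasibility study of 80 patients, no primary outcome uses them, and the sample size is unaffected.

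**What to change.** 1. In the Synopsis and section 2.4.6.5, define change as running from the first study score to about 3 and 6 months after the initial visit. The first study score is the first completed survey or, for Katz, Lawton and the two physical tests, the first virtual visit. Do not describe the result as change from discharge.
2. Report the distribution of days from discharge to the first score, and include those days as a covariate in the group comparisons of change. Fix this before the data are seen.
3. Move age to the continuous variables analysed by ANCOVA, and plot change against age, because a linear term can miss a curved relation. If bands are wanted for display, state them in advance.

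Cost: rewording two sections and one extra covariate in each group comparison. The discharge date is already in the enrollment log; the date each first score is completed must be kept with it. No visit, questionnaire or patient is added. The covariate does not alter the within-patient Wilcoxon results, so those should be read beside the reported days. Physical tests are done only in willing and able patients, so those models may have fewer than 80.
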